4.2.1.1 Definition of the MTCA

Several radioactivity amounts of ¹⁷⁷Lu-3BP-227 are planned to be tested according to an adaptive radioactivity escalation plan. Each subject will only participate in one part of the protocol. The purpose of the radioactivity escalation part is to determine the MTCA. If not feasible, the maximum tolerated single activity (MTSA) or the maximum administered cumulative activity (MACA) will be determined according to the situation below:

- The MTCA is defined as the maximum tolerated cumulative activity that may be administered following fractionated i.v. administrations of at least 4 weeks apart, so that:
 - No more than 33% of the subjects experience a DLT during Cycles 1 and/or 2 (see DLT definition in Section 4.7.1.1), and
 - The cumulative radiation in each target organ does not exceed the acceptability limits (see Section 4.7.1).
- The MTSA is defined as the highest single radioactivity that can be given so that no more than 33% of the subjects experience a DLT during Cycle 1. The MTSA will be determined in case of unacceptable toxicity seen after Cycle 1.
- The MACA will be determined if the MTCA is not reached during the dose escalation part.

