4.7.1.3 Replacement Rules

In phase I, a cohort will be considered as completed once three subjects of the cohort complete Cycle 2 or discontinue early during Cycle 2 (except for Cohort 1). Except for Cohort 1, if subjects discontinue for any reason other than a DLT (e.g. disease progression) before end of Cycle 2, they may be replaced.

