12.1 Analysis Sets

For dose escalation only, all subjects who complete Cycle 2 or discontinue during Cycle 1 or Cycle 2 due to a DLT will be included in the MTCA and MTSA evaluations.

For the overall study, all subjects who received at least one dose of the IMP will be included in the safety evaluation. All subjects who receive at least one dose of IMP and who have postbaseline efficacy data will be included in the efficacy evaluations. All subjects with evaluable 3BP-227 PK data and no major protocol deviation with an impact on PK analysis will be included in the evaluation of 3BP-227 PK. All subjects with evaluable dosimetry images and no major protocol deviation with an impact on dosimetry analysis will be included in the evaluation of dosimetry. All subjects with evaluable blood or urine dosimetry data and no major protocol deviation with an impact on ¹⁷⁷Lu-3BP-227 PK analysis will be included in the evaluation of ¹⁷⁷Lu-3BP-227 PK. Major deviations will be described in a specific document.

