19.5.1 Statistical Model

After study screening procedures, eligible subjects will receive up to 2 i.v. administrations of 177 Lu-3BP-227 in two consecutive treatment cycles 4 weeks apart. A range of doses will be tested, including possibly 2.5, 3, 3.5, 4, 4.5, 5, 5.5, 6, 6.5, 7 and 7.5 GBq per cycle. Additional or alternative dose levels may be chosen. These possible dose levels are labelled as d=1, ..., N, where N is the maximum number of dose levels for the study.

The analysis is based on a method reported by Guede et al.[9] and Tibaldi et al. [37].

If, during Cycle 1, a subject receives dose d_1 and in Cycle 2 dose d_2 , the probability, p, of observing a subject with DLTs up to 4 weeks after the two cycles of dosing is modelled as a function of dose as:

logit
$$(p) = \text{logit } (p_0) + \frac{\text{logit } (33\%) - \text{logit } (p_0)}{MTSA} d_1 + \beta * d_2$$

where p_0 , MTSA and β are the model parameters having the following interpretation:

- p_0 is the probability of observing DLTs under placebo ($d_1=d_2=0$),
- MTSA is the maximum tolerated single activity, being defined as the dose d₁ at which the predicted probability of DLTs is 33% for dosing Cycle 1 (single dose), and
- β is a slope coefficient indicating the impact of a second dose d_2 on DLT probability.

The prior distribution on p_0 , MTSA and β determine the prior distribution on the probability of DLT as a function of up to two doses. For cycle 1 data analysis, the dose d_2 is set to zero. So, only parameters p_0 and MTSA are involved. β is involved when subjects undergo their second cycle. A positive β indicates an increase in DLT probability with second dose.

The MTCA is defined as the maximum tolerated cumulative activity $(d=d_1+d_2)$, where $d_1=d_2$) that may be administered following fractionated i.v. administrations of the same dose d_1 at least 4 weeks apart so that no more than 33% of the subjects experience a DLT during Cycles 1 and/or 2.

The MTCA can be presented as a derived parameter from the logistic regression model. It is expressed as:

$$MTCA = 2* MTSA * \frac{\text{logit } 33\% - logit }{\text{logit } 33\% - \text{logit } p_0 + \beta * MTSA}.$$

The MTCA will be equal to twice the MTSA when β equals 0 (i.e. the DLT probability is not changed after a second dose). When the DLT probability is increased (β >0), the MTCA will be decreased (and vice versa).

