19.5.2 Trial Simulation Details

This section present results of trial simulation study that was performed to determine the operational characteristics of the adaptive dose escalation procedure. The design of that simulation study is very similar to the actual study design, with some changes necessary to enable the automation of trial simulations. The impact of any discrepancy should be negligible.

The trial design involves two sets of rules, namely:

- (1) dose-escalation rules for the next cohort when the current cohort completes Cycle 2, and
- (2) rules for Cycle 2 dosing after completion of Cycle 1.

A cohort will be considered as ended once three subjects of the cohort complete Cycle 2 or early discontinue during Cycle 2. Subjects with DLTs in Cycle 1 will be discontinued prior to Cycle 2.

Once five subjects are enrolled in a cohort, the cohort will be considered as ended, after all five subjects complete Cycle 2 or discontinue early during Cycle 1 or 2.

For the purpose of simulations, the dose decisions will be made at the following milestones:

- Cycle 2 dosing will be determined only once the full cohort, including any replacement subjects, completes Cycle 1 (as opposed to on an individual basis in the study).
- The dose for the next cohort will be decided once the current cohort has ended.

The timing of these decisions will slightly vary during the study, as it is currently planned to decide the Cycle 2 dose on an individual subject basis and to decide for the next cohort once up to three subjects in the current cohort are 3 weeks into Cycle 2. The impact of these changes should be minimal.

The inter cohort dose escalation will be performed as follows:

- (1) The starting dose will be d=5 GBq fractionated into two administrations of $d_1=d_2=2.5$ GBq per cycle and the first cohort will include three subjects.
- (2) If there is no DLT during Cycle 1, the radioactivity for the next cohort will be increased by 3 GBq (1.5 GBq/cycle) up to 11 GBq (5.5 GBq/cycle) and then by 2 GBq (1 GBq/cycle) up to the last planned cohort of 15 GBq (7.5 GBq/cycle). Cohort size will be three subjects.
- (3) If at least one subject in a cohort reports any DLT, wait for the corresponding cohort (including any replacement) to end the study, then fit the Bayesian model to all available Cycle 1 and Cycle 2 data, and select next dose as the dose d at which QS_d is maximum, or the maximum allowed dose if any of the following constraints are met:

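### The analysis set for the maximum tolerated single activity (MTSA) requires Cycle 2 completion, which drops DLT-free Cycle 1 completers and biases the final MTSA estimate downward

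*Protocol*

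**What the plan says.** Protocol section 12.1 sets one rule for the MTSA and for the maximum tolerated cumulative activity (MTCA). In dose escalation, it covers those "who complete Cycle 2 or discontinue during Cycle 1 or Cycle 2 due to a DLT will be included in the MTCA and MTSA" analyses.

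Section 4.2.1.1 defines the MTSA as the "highest single radioactivity that can be given so that no more than 33% of the subjects experience a DLT during Cycle 1", and says when it is needed: "The MTSA will be determined in case of unacceptable toxicity seen after Cycle 1". The model in section 19.5.1 follows that definition: "For cycle 1 data analysis, the dose d_2 is set to zero". It continues: "So, only parameters p_0 and MTSA are involved".

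Section 4.7.1.3 expects some subjects to leave without a DLT. Outside Cohort 1, "if subjects discontinue for any reason other than a DLT (e.g. disease progression) before end of Cycle 2, they may be replaced".

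Section 12.2.4 plans the final analysis as a Bayesian logistic regression, if feasible, with MTSA and MTCA both derived from its parameters. For escalation, Attachment 5 (section 19.5.2) says to wait for the cohort to end after a DLT, "then fit the Bayesian model to all available Cycle 1 and Cycle 2 data".

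SAP section 2 defines no MTSA or MTCA set. The SAP does not describe the final Bayesian estimation, and its section 5 reports no changes from the protocol.

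**The concern.** Nothing that happens in Cycle 2 is needed to know whether a subject had a DLT in Cycle 1. Under section 12.1, a DLT-free subject still counts toward the MTSA only by completing Cycle 2 or by stopping for a DLT in Cycle 2. A subject with a Cycle 1 DLT enters at once, because a DLT ends treatment (section 4.7.1). So removal depends on the outcome: the Cycle 1 information that is lost comes from non-events.

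At stake is the final MTSA from section 12.2.4, which is the fallback limit when the MTCA cannot be determined. It would be understated, and it would not match the estimate that guided the escalation, because the two are fitted to different subjects. In section 19.5.1 the MTCA is a function of the MTSA, p0 and beta, so an error in the MTSA can carry into an MTCA taken from the same fit. How far depends on beta, and that was not quantified here.

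**Working it through.** **Who enters the MTSA evaluation**

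| Subject | Cycle 1 outcome known | In the section 12.1 set |
|---|---|---|
| Stops for a DLT in Cycle 1 | yes, event | yes |
| No DLT in Cycle 1, stops for a DLT in Cycle 2 | yes, non-event | yes |
| No DLT in Cycle 1, completes Cycle 2 | yes, non-event | yes |
| No DLT in Cycle 1, then stops for another reason before the end of Cycle 2 | yes, non-event | **no** |

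Subjects who leave during Cycle 1 without a DLT have an incomplete Cycle 1 window. Leaving them out is a separate matter.

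**Inputs**

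- Target DLT rate 33%, Cycle 1 only (section 4.2.1.1).
- Model with d2 = 0: logit(p) = logit(p0) + [logit(0.33) − logit(p0)] × d1 / MTSA (section 19.5.1).
- Scenario C: true MTSA 7 GBq (section 19.5.3).
- p0 = 5%. Section 19.5.4 gives this as the starting value of the sampler; it is assumed here to be the simulated truth.
- w, the share of DLT-free Cycle 1 completers who do not complete Cycle 2 for non-DLT reasons. The documents give no phase I value. The range 10% to 30% is assumed. The only related figure is the 20% non-evaluability rate in section 12.3.1, which is for phase II.

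**Step 1: reproduce the plan's figures.** For Scenario C, Cycle 1, 2.5 to 7.5 GBq, the model gives 10.5, 12.1, 13.9, 15.9, 18.1, 20.6, 23.4, 26.4, 29.6, 33.0 and 36.6%. Table 12 has 10, 12, 14, 16, 18, 21, 23, 26, 30, 33 and 37%. All agree within 0.5 point.

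**Step 2: apparent Cycle 1 rate under section 12.1.** Events keep weight p; non-events are thinned to (1−p)(1−w):

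apparent rate = p / [p + (1−p)(1−w)]

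For p = 20% and w = 20%: 0.20 / (0.20 + 0.80 × 0.80) = 0.20 / 0.84 = 23.8%.

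The true rate that reads as 33% is 0.33(1−w) / [0.33(1−w) + 0.67]. For w = 20%: 0.264 / 0.934 = 28.3%.

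**Step 3: effect on the MTSA without priors.** The apparent odds are the true odds divided by (1−w), so the logit rises by −ln(1−w) at every activity. With K = logit(0.33) − logit(0.05) = −0.708 + 2.944 = 2.236, the apparent curve reaches 33% at 7 × [1 + ln(1−w)/K] GBq. For w = 20%: 7 × (1 − 0.223/2.236) = 6.3 GBq. This takes w as equal at all activities.

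| w (assumed) | True 20% reads as | True 33% reads as | True rate that reads as 33% | Apparent MTSA (true 7.0 GBq) |
|---|---|---|---|---|
| 10% | 21.7% | 35.4% | 30.7% | 6.7 GBq |
| 20% | 23.8% | 38.1% | 28.3% | 6.3 GBq |
| 30% | 26.3% | 41.3% | 25.6% | 5.9 GBq |

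**Step 4: effect with the protocol priors.** Take the section 19.5.1 priors, beta(1, 9) for p0 and gamma(4, rate 0.5) for the MTSA, and invented Cycle 1 data: DLTs in 0/3, 0/5, 1/5, 1/5 and 1/5 subjects at 2.5, 4, 5.5, 6.5 and 7.5 GBq. The posterior median MTSA is 9.5 GBq. Removing one DLT-free subject from each cohort of five gives 8.8 GBq; removing two gives 7.9 GBq. The direction is the same and the priors temper the size. In this example all three medians lie above the top planned single activity of 7.5 GBq.

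**The case against.** The strongest reply is that little depends on this set. Four points deserve an answer.

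- **Escalation.** A reader might infer that dose selection and stopping are distorted, since Attachment 5 uses MTSA quantities for both. The documents do not support that. Attachment 5 fits all available data, its DLT-count limits refer to subjects receiving a dose, and the safety review committee sees all cumulative information (section 12.2.8). If Attachment 5 is followed, escalation is unaffected.
- **Reported DLT rates.** A reader might also infer that the DLT tables are inflated. SAP section 3.2.1 bases safety summaries on the safety population, with no Cycle 2 filter.
- **A single cohort.** With five treated, one Cycle 1 DLT and two later non-DLT stops, 1/5 becomes 1/3, which looks like a breach of 33%. No rule compares a raw cohort proportion with 33%. The count limits in section 19.5.2 start at two of three and three of five, and the MTSA comes from a model.
- **Dropout.** Scheduled CT/MRI in the core trial is only at screening and at the end of core trial visit (Table 8), and entry requires a life expectancy above 3 months. Progression before the end of Cycle 2 would have to surface clinically or on unscheduled imaging, so w may be small. It is not zero by design: section 4.7.1.3 names progression as a reason to stop, and optional replacement does not return the lost non-event to the set.

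It is also fair to say that the Cycle 2 condition is defensible for the MTCA, that the MTSA is a fallback, and that the primary endpoint is the MTCA or the maximum administered cumulative activity. These points limit the reach. They do not explain why a Cycle 1 quantity should need Cycle 2 completion.

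**Conclusion.** The point stands for the final MTSA estimate in section 12.2.4. The direction, a higher apparent Cycle 1 DLT rate and a lower MTSA, follows from the wording for any w above zero. The size rests on an assumed w. At 10% to 30% a true 20% reads as 21.7% to 26.3%, and at w = 20% a true 28.3% reads as 33%. The model-based MTSA moves less simply, because the priors pull on it.

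It would go too far to say that every DLT is retained. Section 12.1 ties inclusion to the reason for discontinuation, so a subject with a DLT whose recorded reason was something else, and who did not complete Cycle 2, would be left out. In practice DLT subjects should enter, because a DLT stops treatment.

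Sections 4.2.1.1, 12.1 and 12.2.4 and Attachment 5 should be reconciled before the final analysis.

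**What to change.** - **Protocol 12.1.** Define the MTSA evaluation set as all subjects who complete the Cycle 1 observation period or have a DLT in Cycle 1, whatever happens later.
- **Protocol 12.2.4.** Fit one joint model to all available data, as Attachment 5 does. Two separate sets cannot be carried into one fit, because the MTCA is a function of the MTSA, p0 and beta from that fit. The Cycle 1 outcome enters at d2 = 0, including for subjects without an evaluable Cycle 2. The Cycle 2 outcome enters for subjects who complete Cycle 2 or have a Cycle 2 DLT. MTSA and MTCA are both derived from this fit.
- **SAP.** Add the set and the model, since it has neither. Write out each subject's contribution to the likelihood, so that the DLT-free first cycle of those who complete Cycle 2 also counts toward the MTSA. If the d2 = 0 records came only from Cycle 1 DLTs and early stops, a selection on outcome would return.

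The cost is a short text change in the protocol, a new paragraph or two in the SAP and minor programming. The data are already collected; no additional subjects or procedures are needed.

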12.2 Statistical Methodology for Phase I

12.2.1 Sample Size Calculation

12.2.1.1 Dose Escalation

As this is primarily a descriptive safety and tolerability study, the total number of subjects is not based on a formal statistical sample size calculation.

For the dose escalation part, the actual sample size required to adequately determine the MTCA/MTSA during dose escalation depends on the initial dose, rate of dose escalation and the observed dose-toxicity and dose/radiation exposure relationships. Simulation studies have been performed to quantify the operational characteristics (i.e. precision of the MTCA/MTSA, sample size, number of subjects being over/under dosed) of the adaptive dose-escalation design under a number of plausible dose-DLT relationship scenarios. Results are provided in Attachment 5, Section 19.5. Based on experience, the chosen sample size of three to five subjects per cohort is considered sufficient to fulfil the objectives of the study. It is anticipated that approximately 30 subjects will be required to establish the MTCA or MACA.

12.2.1.2 Dose Expansion

If safety evaluation of ¹⁷⁷Lu-3BP-227 and dose schedules cannot be fully explored during the phase I dose escalation part, a phase I expansion part enrolling up to 45 subjects will serve to accomplish this objective including, but not limited to, schedules of high loading doses followed by fractionated lower doses or evaluation of ¹⁷⁷Lu-3BP-227 in combination with other antitumoral treatments (to be defined). The expansion part will also serve to clarify any uncertainties of antitumour responses. The sample size will be specified in a protocol amendment.

12.2.2 Statistical Methods

Details of the statistical analysis will be specified in the statistical analysis plan (SAP). The statistical analyses will be conducted using Statistical Analysis System. Summary descriptive tables, by RL, will be provided.

Continuous data will be summarised with the following items: frequency, median, range, mean and coefficient of variation (CV) if relevant.

Categorical data will be presented in contingency tables with frequencies and percentages of each modality (including missing data modality). The 95% confidence interval will be calculated following the exact method.

To describe time dependent parameters (PFS, OS), Kaplan-Meier curves and life tables will be provided. The 95% confidence interval of the median will be given.

An overview of the main analysis strategy is provided in the following sections.

12.2.3 Demographic and Other Baseline Characteristics

Summary statistics will be presented for the total study population and by cohort. Frequency tables for qualitative data will be provided. Medical and surgical history findings will be summarised using MedDRA terms.

12.2.4 Maximum Tolerated Single and Cumulative Activity

Individual listings and treatment summaries of DLTs with NCI-CTCAE code and grade will be presented.

The incidence of subjects with DLTs during Cycles 1 or 2 will be summarised by treatment and, if possible, modelled as a function of the fractional doses for Cycles 1 and 2 using Bayesian logistic regression. The moderately-informative independent priors used during the interim analysis (see Attachment 5, Section 19.5 for details) as well as noninformative priors will be used for this analysis in order to assess sensitivity of the estimates. Parameter estimates and model predictions will be reported with 90% credibility sets. The MTCA and MTSA will be computed as a derived function of model parameters.

The posterior distribution of the MTCA and MTSA will be summarised in tabular and graphical formats.

The number of subjects with at least one DLT or NCI-CTCAE Grade ≥2 (excluding hair loss) will be tabulated by RL by cycle and overall. The type of DLT and NCI-CTCAE Grade ≥2 will also be presented.

12.2.5 Safety Evaluation

For the overall study, descriptive statistics will be calculated on the safety parameters. No formal statistical analyses of safety data are planned.

Summaries will be prepared by treatment group and, as needed, by timepoint.

All AEs will be coded according to the latest version of the MedDRA and NCI-CTCAE.

Study drug TEAE summaries will include the overall incidence (by system organ class (SOC) and preferred term (PT)), events by maximum intensity, events by relationship to study drug, events leading to discontinuation of study drug and SAEs.

Physical examination findings, vital signs, ECG 3-lead 24h Holter recordings and clinical laboratory parameters will be summarised descriptively at each timepoint. Actual and change from baseline data will be calculated and summarised where data are available. The investigator's interpretation of 12-lead ECGs will be listed.

Concomitant medications will be coded using the latest version of the World Health Organization (WHO) drug dictionary and will be summarised by treatment group and overall with the number and percentage of subjects receiving concomitant medication by drug class and preferred drug name.

The NCI-CTCAE version 5.0 classification [31] will be used to classify all TEAEs and laboratory abnormalities.

Maximum grade or severity will be tabulated by subject for each MedDRA SOC and PT. Analyses of AEs and SAEs will be performed in two different ways: regardless of the relationship to the study treatment and related to the study treatment. Moreover, all AEs without SAEs and SAEs only will be tabulated.

For haematological and biochemical toxicities, the worst NCI-CTCAE grade by subject and by cycle will be tabulated and listed. For white blood cells, neutrophils, platelets and haemoglobin, with associated Grade 3 or 4 toxicities, nadir and day to nadir will be calculated.

A TEAE is defined as any AE that occurs during the active phase of the study if:

- It was not present prior to receiving the first dose of ¹⁷⁷Lu-3B-227; or
- It was present prior to receiving the first dose of ¹⁷⁷Lu-3B-227 but the intensity increased during the active phase of the study; or
- It was present prior to receiving the first dose of ¹⁷⁷Lu-3B-227, the intensity is the same but the drug relationship became related during the active phase of the study.

12.2.6 Pharmacokinetics, Biodistribution and Dosimetry

12.2.6.1 Biodistribution and Pharmacokinetic Analysis of ¹⁷⁷Lu-3BP-227

The biodistribution and PK analyses of the radiopharmaceutical ¹⁷⁷Lu-3BP-227 will be performed under the responsibility of the sponsor's Clinical Pharmacokinetics and Pharmacometrics department.

The following biodistribution (i.e. organ PK) parameters will be evaluated:

- maximal uptake (%) at the target lesion
- maximal uptake (%) in discernible organs and blood
- the C_{max} of ¹⁷⁷Lu-3BP-227 in discernible thoracic and abdominal organs, target lesion and blood
- the T_{max} of 177 Lu-3BP-227 in discernible thoracic and abdominal organs, target lesion and blood
- the AUC of ¹⁷⁷Lu-3BP-227 in discernible thoracic and abdominal organs, target lesion and blood
- terminal $t_{1/2}$ of activity concentrations of 177 Lu-3BP-227 in blood.

Data analysis and all biodistribution parameters will be further described in a SAP.

Biodistribution data for target lesion and all abdominal and thoracic organs analysed will be listed for each study subject and each sampling timepoint. In addition, arithmetic mean, arithmetic standard deviation, CV and number of data points will be provided per sampling point. The biodistribution parameters will be estimated for each subject. Total radioactivity cumulatively excreted in the urine in the interval 0 to 6 hours, 6 to 12 hours, 12 to 24 hours and 24 to 48 hours postinfusion will be determined for each subject.

Measured total ¹⁷⁷Lu-3BP-227 radioactivity concentrations in whole blood and urine will be listed for each study subject and each sampling time point. In addition, means, standard deviation, CV and number of data points will be provided per sampling point. Based on the individual ¹⁷⁷Lu-3BP-227 blood time-activity curves, the concentration-time profiles of ¹⁷⁷Lu-3BP-227 and the AUC in blood, will be estimated for each subject.

